6.1.7.4. Impact of induction of sample on sputum bacterial results

The impact of sputum induction on the bactericidal culture or PCR results will be evaluated, for stable (scheduled) visits, exacerbation visits, or any visit.

6.1.7.5. Impact of previous occurrence of Hi bacterial pathogen in sputum on AECOPDs

The impact of the occurrence or presence of respiratory pathogenic bacteria detected in sputum at the exacerbation visit given the presence of the bacteria at previous visits on the number of exacerbations will also be studied. In order to do this, 2 types of AECOPDs will be distinguished:

- AECOPDs in which Hi is present and was not present any previous visit
- AECOPDs in which Hi is present and was not present in the previous stable visit;

7. STATISTICAL CALCULATIONS

7.1. Derived and transformed data

The study groups will be defined by treatment actually administered at Dose 1.

7.1.1. Demography

- For a given subject and a given demographic variable, missing measurement will not be replaced.
- Age: Age at the reference activity, computed as the number of units between the date of birth and the reference activity In case of partial dates of any of these 2 dates:
 - 15th of month, If only the day is missing

Statistical Analysis Plan

Study alias & e-track number(s): NTHi-004 (200157)

- 30th of June, if day and months are missing

7.1.2. Safety

- For solicited symptoms, the analysis will exclude subjects with missing or un-evaluable measurements (*i.e.* total analysis of solicited symptoms will include all vaccinated subjects with documented solicited symptom sheets).
- For the unsolicited symptoms and concomitant medications/ products/ vaccinations, subjects who miss reporting symptoms/concomitant medications/ products/ vaccinations will be treated as subjects without unsolicited symptoms or concomitant medications/ products/ vaccinations, respectively.
- Note that for all tables described in this section, the way the percentage of subjects will be derived will depend on the event analysed (see table below for details). As a result, the N value will differ from one table to another.

Event	N used for deriving % per subject
Concomitant vaccination	All subjects with study vaccine administered
Solicited general symptom	All subjects with at least one solicited general symptom documented as either present or absent (i.e. symptom screen completed)
Solicited local symptom	All subjects with at least one solicited local symptom documented as either present or absent (i.e. symptom screen completed)
Unsolicited symptom	All subjects with study vaccine administered
Concomitant medication	All subjects with study vaccine administered

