11.6. Derived and transformed data

The study groups will be defined by treatment actually administered at Dose 1.

Demography

- For a given subject and a given demographic variable, missing measurement will not be replaced.

Safety

- For solicited symptoms, the analysis will exclude subjects with missing or un-evaluable measurements (*i.e.* total analysis of solicited symptoms will include all vaccinated subjects with documented solicited symptom sheets).
- For the unsolicited symptoms and concomitant medications/ products/ vaccinations, subjects who miss reporting symptoms/concomitant medications/ products/ vaccinations will be treated as subjects without unsolicited symptoms or concomitant medications/ products/ vaccinations, respectively.

Immunogenicity

- For a given subject and the analysis of a given immunogenicity measurement, missing or un-evaluable measurements will not be replaced.
- A seronegative subject is defined as a subject whose antibody concentration is below the assay cut-off value.
- A seropositive subject is defined as a subject whose antibody concentration is greater than or equal to the assay cut-off value.
- Antibody concentrations below the assay cut-off will be given an arbitrary value of half the assay cut-off for the purpose of geometric mean concentration (GMC) calculation.

- Calculation of the GMCs will be performed by taking the anti-logarithm in base 10 (anti-log10) of the mean of the log10 concentration transformations.

Impact of the investigational vaccine on AECOPD

- For a given subject and the analysis of a given laboratory assay, missing or un-evaluable measurements will not be replaced.
- Subjects who did not have any sputum collected during at least 1 AECOPD (if at least 1 AECOPD occurred) will not be taken into account for the NTHI-associated AECOPD analyses.

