4. ENDPOINTS

4.1. Primary endpoints

- Occurrence of each solicited local adverse event (AE), during the 7-day follow-up period (*i.e.* day 0 - 6) following each vaccination, in all subjects.
- Occurrence of each solicited general AE, during the 7-day follow-up period (*i.e.* day 0 - 6) following each vaccination, in all subjects.
- Occurrence of any unsolicited AE, during the 30-day follow-up period (*i.e.* day 0 - 29) following each vaccination, in all subjects.
- Occurrence of each haematological/ biochemical laboratory abnormality at Day 0, Day 7, Day 30, Day 60, Day 67, Day 90, Day 270 and Day 450, in all subjects.
- Occurrence of any potential immune-mediated disease (pIMD) from first vaccination up to study conclusion, in all subjects.

Statistical Analysis Plan

Study alias & e-track number(s): NTHi-004 (200157)

- Occurrence of any serious adverse event (SAE) from first vaccination up to study conclusion, in all subjects.

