6.1.1. Analysis of safety

The analysis will be performed on the TVC. If the percentage of vaccinated subjects excluded from the ATP cohort for efficacy is at least 10%, a second analysis will be performed on the ATP cohort for efficacy to complement the first analysis.

The percentage of subjects with at least one **local AE** (solicited and unsolicited), with at least one **general AE** (solicited and unsolicited) and with any AE during the 7-day (day 0 – day 6) or the 30-day (day 0 – day 29) follow-up period will be tabulated after each

Statistical Analysis Plan

Study alias & e-track number(s): NTHi-004 (200157)

vaccination and overall with exact 95% confidence interval (CI). The same computations will be done for Grade 3 AEs, for related AEs and for Grade 3 related AEs.

The percentage of subjects/doses reporting each individual solicited local (any grade, Grade 3) and general (any grade, Grade 3, related, Grade 3 related) AE during the 7-day (day 0 to day 6) follow-up period will be tabulated for each group as follows:

- Overall, the percentage of subjects with the symptom and its exact 95% CI.
- Overall, the percentage of doses with the symptom and its exact 95% CI.
- Per study vaccine dose, the percentage of subjects with the symptom and its exact 95% CI.

The exact 95% CIs will be calculated assuming independence between doses. For fever, additional analyses will be performed by 0.5°C increments.

As during the study, some subjects have completed wrong diary cards (paediatric ones instead of adults), a sensitivity analysis will be done on subjects that have completed the correct diary cards to be sure that they were no impact on results.

The verbatim reports of **unsolicited** symptoms will be reviewed by a physician and the signs and symptoms will be coded according to the MedDRA Dictionary for Adverse Reaction Terminology. Every verbatim term will be matched with the appropriate preferred term (PT). The percentage of subjects with unsolicited symptoms during the 30-day follow-up period after any study vaccine dose with its exact 95% CI will be tabulated by group and by MedDRA PT. Similar tabulation will be done for the percentage of doses, for Grade 3 unsolicited symptoms, for unsolicited symptoms that resulted in a medically attended visit, for Grade 3 and causally related unsolicited symptoms and for unsolicited symptoms causally related to vaccination.

For each group and for each **haematology/ biochemistry parameter**:

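### A vaccinated subject with no unsolicited AE report is counted as AE-free over days 0-29, which can only lower a primary-endpoint incidence, and no planned analysis addresses missing reports

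*SAP*

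**What the plan says.** One of the primary endpoints is "Occurrence of any unsolicited AE, during the 30-day follow-up period" after each dose (SAP 4.1; Protocol 11.1). SAP 6.1.1 tabulates "The percentage of subjects with unsolicited symptoms during the 30-day follow-up period after any study vaccine dose" by group and preferred term, with an exact 95% CI.

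For missing reports, SAP 7.1.2 states that "subjects who miss reporting symptoms/concomitant medications/ products/ vaccinations will be treated as subjects without unsolicited symptoms". Protocol 11.6 has the same rule: such subjects "will be treated as subjects without unsolicited symptoms". The table of denominators in SAP 7.1.2 sets N for unsolicited symptoms as "All subjects with study vaccine administered".

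The preceding bullet of SAP 7.1.2 goes the other way: "For solicited symptoms, the analysis will exclude subjects with missing or un-evaluable measurements". The summary in SAP 6.1.1 of subjects with a local AE, with a general AE "and with any AE during the 7-day" or 30-day period combines both kinds of event. The denominator table has no row for that combination.

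The only safety sensitivity analysis (SAP 6.1.1 and section 9) concerns subjects who filled in paediatric diary cards. The conditional second safety analysis uses the ATP cohort for efficacy, whose criteria (SAP 5.4) do not require complete AE reporting.

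**The concern.** The rule turns absence of information into absence of an event. The percentage it yields is the share of vaccinated subjects with a reported AE. It equals the 30-day incidence only if nobody who is silent had an event. Describing safety is the trial's sole primary objective, and the percentages with their intervals are the result, so the direction of the error matters: it always favours a lower figure.

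The plan also hides the extent of the problem. Withdrawals are tabulated by reason, but no table shows how many subjects had documented follow-up through day 29 after each dose, so a reader could not recover the observed denominator. For the tertiary exacerbation endpoints, by contrast, SAP 6.1.3 does account for incomplete follow-up, through a follow-up-time offset.

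**Working it through.** **Inputs.** About 70 subjects per group, 1:1 (Protocol 5.1 and 6.2.2.2.1). Exact two-sided 95% CIs (SAP 6.1.1, 7.1.3 and 10). Non-reporters stay in N as event-free (SAP 7.1.2). Neither a non-reporting rate nor an expected AE incidence is stated, so both are assumed below.

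**1. The plan's own figure.** Protocol 11.4 gives the chance of seeing at least one case among 70 subjects as more than 50% at a true incidence of 1% and more than 97% at 5%. The formula is 1 − (1 − p)^n.
- n = 70: 1 − 0.99^70 = 0.505 and 1 − 0.95^70 = 0.972. Both figures reproduce.
- n = 69 (one silent subject): 0.500 (0.5002 unrounded) and 0.971, still just above.
- n = 68 (two silent subjects): 0.495 and 0.969. Both fall below the stated figures.

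A silent subject cannot contribute a detected event. No re-analysis restores this loss, but it shows why the observed number should be reported.

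**2. One group.** Take 70 vaccinated, 28 with a reported AE and 7 with no report (assumed).
- Under the rule: 28/70 = 40.0% (exact 95% CI 28.5 to 52.4).
- Among the 63 with reports: 28/63 = 44.4% (31.9 to 57.5).
- Possible range: from 28/70 = 40.0% if none of the 7 had an event to (28 + 7)/70 = 50.0% if all did. The rule always reports the bottom of this range.
- A rarer event: 7/70 = 10.0% (4.1 to 19.5) against 7/63 = 11.1% (4.6 to 21.6).
- No events: the exact upper limit is 5.1% with 70 and 5.7% with 63.

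**3. The contrast.** If a share m of a group is silent and silence is unrelated to AE risk, the tabulated rate is p(1 − m). With assumed true rates of 40% (vaccine) and 25% (control):

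| Silent, vaccine / control | Tabulated rates | Difference (points) | Risk ratio |
|---|---|---|---|
| 0% / 0% | 40.0% vs 25.0% | 15.0 | 1.60 |
| 10% / 10% | 36.0% vs 22.5% | 13.5 | 1.60 |
| 10% / 0% | 36.0% vs 25.0% | 11.0 | 1.44 |
| 0% / 10% | 40.0% vs 22.5% | 17.5 | 1.78 |

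Hiding this excess completely would need 1 − 0.25/0.40 = 37.5% silent in the vaccine group and none in control.

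**4. Non-reporting related to AE risk.** Suppose the true rate is 40%, 10% are silent and the silent have a 60% risk. Reported events are 0.40 − 0.10 × 0.60 = 0.34 of the group. The rule shows 34%; the documented denominator gives 0.34/0.90 = 37.8%. That is closer to 40% but still low.

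**The case against.** Counting AEs over all vaccinated subjects is a common convention, the trial is descriptive (Protocol 11.14.2), and the Protocol glossary defines an unsolicited AE in terms of its being reported. There is also a practical reason for the different handling: a solicited sheet records each symptom as present or absent, so a blank is recognisable, whereas silence about unsolicited events may simply mean there were none. This explains the rule and supports keeping the all-vaccinated row. It does not make silence after loss to follow-up an observation of no event, and in a descriptive trial the label on the percentage matters.

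Three stronger readings are tempting, and the documents do not support them.

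- A reader might infer that anyone who withdraws on day 5, or whose second diary card is lost, is scored AE-free. Data up to withdrawal are used (Protocol 10.2.1), the first card also collects unsolicited events and missing cards are chased (6.6.20), staff ask about events at visits (9.3.3.1), and AEs leading to withdrawal are collected to study end (9.3.1). The rule affects only subjects with no report by any route.
- A reader might infer that the rule masks a vaccine excess. That needs more non-reporting in the vaccine group. The documents give no reason to expect either direction, and AEs leading to withdrawal are also reported separately (SAP 6.1.1).
- A reader might infer that the same imputation governs the combined any-AE summary. SAP 7.1.2 gives no N and no missing-report rule for it. The supportable finding is that this is unspecified while its two components follow opposite rules.

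**Conclusion.** The point stands in limited form. SAP 7.1.2 and Protocol 11.6 impute no event for a vaccinated subject with no unsolicited AE report, so the tabulated incidence of a primary endpoint can only be lowered or left unchanged, and no planned analysis would show by how much. The direction within each group follows from the rule itself. The direction for the vaccine-placebo contrast does not: it depends on which group has more non-reporting.

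The size is unknown. The 40.0% against 44.4% illustration assumes 10% non-reporting, and the second figure estimates the incidence only if loss is unrelated to AE risk. Given the other routes by which events are captured, the true number of silent subjects may be small. Reporting that number is the main thing asked for.

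**What to change.** In SAP 7.1.2, with matching wording in Protocol 11.6:

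1. Keep the all-vaccinated percentage, labelled *subjects with a reported AE*.
2. Report the number with documented day 0-29 AE follow-up by dose and group. Diary-card transcription and AE recording at visits are already eCRF items (Protocol 6.5.1, Table 7). Card return itself is not, so the definition should rest on the first two.
3. Add one sensitivity estimate: the percentage with exact 95% CI on the documented-follow-up denominator, stating how a subject with an event before loss is counted. A Kaplan-Meier cumulative incidence, censored at the last documented AE contact, is an optional alternative that handles such subjects directly. Either way, note that it assumes loss is unrelated to AE risk; it sits beside the planned row and does not replace it.
4. State N and the missing-report rule for the combined any-AE summary.

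The cost is wording and one extra estimate per table, with no new data collection. The sensitivity incidence will be slightly less favourable and its interval slightly wider (in the illustration, 25.6 points wide against 23.9).

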6.1.2. Analysis of safety

The analysis will be performed on the TVC. If the percentage of vaccinated subjects excluded from the ATP cohort for efficacy is at least 10%, a second analysis will be performed on the ATP cohort for efficacy to complement the first analysis.

The percentage of subjects with at least one **local AE** (solicited and unsolicited), with at least one **general AE** (solicited and unsolicited) and with any AE during the 7-day (day 0 – day 6) or the 30-day (day 0 – day 29) follow-up period will be tabulated after each vaccination and overall with exact 95% confidence interval (CI). The same computations will be done for Grade 3 AEs, for related AEs and for Grade 3 related AEs.

The percentage of subjects/doses reporting each individual solicited local (any grade, Grade 3) and general (any grade, Grade 3, related, Grade 3 related) AE during the 7-day (day 0 to day 6) follow-up period will be tabulated for each group as follows:

- Overall, the percentage of subjects with the symptom and its exact 95% CI.
- Overall, the percentage of doses with the symptom and its exact 95% CI.
- Per study vaccine dose, the percentage of subjects with the symptom and its exact 95% CI.

The exact 95% CIs will be calculated assuming independence between doses. For fever, additional analyses will be performed by 0.5°C increments.

As during the study, 22 subjects have completed wrong diary cards (paediatric ones instead of adults), a sensitivity analysis will be done on subjects that have completed the correct diary cards only, to be sure that they were no impact on results.

The verbatim reports of **unsolicited** symptoms will be reviewed by a physician and the signs and symptoms will be coded according to the MedDRA Dictionary for Adverse Reaction Terminology. Every verbatim term will be matched with the appropriate preferred term (PT). The percentage of subjects with unsolicited symptoms during the 30-day follow-up period after any study vaccine dose with its exact 95% CI will be tabulated by group and by MedDRA PT. Similar tabulation will be done for the percentage of doses, for Grade 3 unsolicited symptoms, for unsolicited symptoms that resulted in a medically attended visit, for Grade 3 and causally related unsolicited symptoms and for unsolicited symptoms causally related to vaccination.

Statistical Analysis Plan

Study alias & e-track number(s): NTHi-004 (200157)

For each group and for each **haematology/ biochemistry parameter**:

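### The denominator for each solicited symptom is set at sheet level, so a subject with that symptom undocumented stays in N and in effect counts as symptom-free

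*SAP*

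**What the plan says.** The primary endpoints (protocol 11.1; SAP 4.1) include the occurrence of each solicited local and each solicited general AE in the 7 days after each vaccination. SAP Amendment 1, section 6.1.1, tabulates these symptom by symptom, as percentages of subjects and of doses with exact 95% CIs.

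Section 7.1.2 of the same document has three relevant statements.

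- **Missing-data rule:** "For solicited symptoms, the analysis will exclude subjects with missing or un-evaluable measurements". The sentence then explains itself at sheet level: "total analysis of solicited symptoms will include all vaccinated subjects with documented solicited symptom sheets". Protocol 11.6 has the same text.
- **N table:** for general symptoms, "All subjects with at least one solicited general symptom documented as either present or absent"; for local symptoms, "All subjects with at least one solicited local symptom documented as either present or absent". Both rows equate this with a completed symptom screen. The table covers percentages per subject only and gives no N for percentages per dose.
- **Unsolicited symptoms and concomitant products:** subjects who do not report "will be treated as subjects without unsolicited symptoms or concomitant medications/ products/ vaccinations, respectively". No such rule is written for solicited symptoms.

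On the diary cards, SAP Version 1, section 6.1.2, says that 22 subjects filled in paediatric cards in place of adult ones. Amendment 1 (sections 6.1.1 and 9) gives no number, refers only to some subjects, and plans that "a sensitivity analysis will be done on subjects that have completed the correct diary cards to be sure that they were no impact on results".

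**The concern.** The numerator is counted per symptom and the denominator per sheet. Take a subject whose sheet has temperature recorded and headache blank. One general symptom is documented, so under the N table this subject is in the denominator for headache. Nothing is recorded for headache, so the subject cannot be in the numerator. The percentage moves in the same way as if the subject had answered no.

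The study is descriptive and reactogenicity is part of its sole primary objective, so these percentages and CIs are themselves the result. Any dilution is towards lower reactogenicity. If blank items were unevenly spread between groups, the contrast with placebo would shift as well.

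The wrong cards give a concrete route by which items could be missing. The protocol's items and intensity scales are in Tables 18, 19 and 22. Neither document says which of them the paediatric card captured, and the main analysis has no rule for an item that was not asked or was graded differently.

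**Working it through.** **1. Inputs.** About 70 subjects per group and 140 in total (protocol 5.1 and 6.2.2.2); 22 subjects with paediatric cards (SAP Version 1, 6.1.2); exact Clopper-Pearson 95% CIs (SAP section 10). The documents do not give m, the number of subjects in a group who returned a sheet but have a given symptom missing. It is an assumption below.

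**2. The plan's own figure.** Protocol 11.4 states more than 50% chance of detecting an AE with 1% true incidence, and more than 97% at 5%, with 70 per group.

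- 1 − 0.99^70 = 50.5%
- 1 − 0.95^70 = 97.2%

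Both are reproduced.

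**3. Share affected.** 22/140 = 15.7%, taking the target enrolment as the base.

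**4. Dilution.** If the symptom is missing for m of 70 subjects, and those with data have true incidence p, the expected reported value is p × (70 − m)/70.

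| Assumption | m | Multiplier | 20% becomes | 30% becomes | 40% becomes |
|---|---|---|---|---|---|
| No item missing | 0 | 1 | 20% | 30% | 40% |
| All 22 lack the item, split 11 and 11 | 11 | 59/70 = 0.843 | 16.9% | 25.3% | 33.7% |

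The incidences are illustrative. For the overall per-subject percentage, the second row also requires that the item was lost at both doses.

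An uneven split would dilute one group more than the other. The arithmetic limit is all 22 in one group: 48/70 = 0.686, so a true 30% is reported as 20.6%, a gap of 9.4 points from an unaffected group with the same true rate. Nothing in the documents points to such a split.

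**5. Effect on an interval.** With m = 11 and 18 subjects reporting the symptom:

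- symptom-specific N: 18/59 = 30.5% (95% CI 19.2 to 43.9)
- sheet-level N: 18/70 = 25.7% (95% CI 16.0 to 37.6)

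The sheet-level interval is both lower and narrower, because it credits information that was not collected.

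**6. What the denominator does not change.** With 59 informative subjects, the detection probabilities in step 2 become 44.7% and 95.2%. That loss comes from the missing data, and no choice of N restores it. A symptom-specific N only makes it visible.

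**The case against.** **The SAP does not say that a missing solicited symptom counts as absent.** A reader might infer that it does. An explicit rule of that kind is written only for unsolicited symptoms and concomitant products, and the bullet before it says that missing measurements are excluded. This stands as a matter of wording: the effect is an arithmetic consequence of the N table. It does not remove the problem, because the bullet's own explanation and both table rows work at sheet level, and no per-symptom N is given anywhere. A programmer following the table would produce the diluted percentage.

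**No omitted item is shown.** A reader might infer from the 22 paediatric cards that protocol symptoms went unasked and that the main percentages are therefore biased. No passage describes the content or scale of those cards, their distribution between groups, or which dose was affected. The count itself appears only in SAP Version 1. The size of the effect is therefore conditional, and may be zero.

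**Sites check the cards.** Under protocol 6.6.20, cards are collected, verified in discussion with the subject and transcribed to the eCRF, and unreturned cards are sought. This should make blanks on adult cards uncommon. It does not correct the rule for blanks that remain.

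**The wrong cards are disclosed, and a sensitivity analysis is planned.** True, and it addresses the wrong-card subjects. It leaves the main estimate as it is and keeps the same denominator rule for adult cards.

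**A differently graded item is still a valid yes or no.** This stands. Setting every such item to missing would discard valid data on an occurrence endpoint, so the correction must not do that.

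**The comparisons are descriptive (protocol 11.13).** No hypothesis test or sample-size figure depends on this point.

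**Conclusion.** The point holds as a defect in a stated rule. In SAP Amendment 1, the sheet-level N in section 7.1.2 does not match the symptom-level percentages in section 6.1.1, and it conflicts with the statement in 7.1.2 that missing measurements are excluded. Where a symptom is undocumented on an otherwise completed sheet, the reported percentage is too low and its CI is misplaced.

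The size is not known. For the wrong cards it runs from no bias to a multiplier of about 0.84 in each group, assuming that the count of 22 still applies, enrolment is near 140, all 22 lacked the item at every dose, and they were split evenly. An uneven split would make one group worse. Blanks on adult cards would add to this by an amount that the documents do not allow one to estimate. They do not support the stronger conclusion that the reactogenicity results are biased. They support the conclusion that the rule permits bias in a primary endpoint and should be corrected.

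**What to change.** - **SAP 7.1.2, N table:** define N for each solicited symptom as the subjects with that symptom documented as present or absent. Add a matching definition for dose-level percentages: doses with that symptom documented as present or absent. Align the missing-data bullet with this.
- **SAP 6.1.1, main analysis:** treat an item that a paediatric card did not ask as missing for that symptom. Where the item was asked but graded on another scale, keep it in the any-grade percentage and treat it as missing only in the Grade 3 tables.
- **Disclosure:** list which protocol symptoms and grades the paediatric card captured, restore the number of affected subjects and give it by group, and report the number missing for each symptom.
- **Sensitivity analysis:** keep the planned analysis on subjects with correct cards.

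The cost is SAP wording and a small amount of programming. N will vary between symptoms within a table, and CIs will be slightly wider for affected items.
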